### 6.3.5 Dosimetry

### 3D Conformal Planning

Three-dimensional coplanar or non-coplanar beam arrangements will be custom designed for each case to deliver highly conformal prescription dose distributions. Non-opposing, non-coplanar beams are preferable. Typically,  $\geq 10$  beams of radiation will be used with roughly equal weighting. Generally, more beams are used for larger lesion sizes. When static beams are used, a minimum of seven non-opposing beams should be used. For arc rotation techniques, a minimum of 340 degrees (cumulative for all beams) should be utilized.

For this protocol, the isocenter is defined as the common point of gantry and couch rotation for the treatment unit. Field aperture size and shape should correspond nearly identically to the projection of the PTV along a beam's eye view (i.e., no additional "margin" for dose buildup at the edges of the blocks or MLC jaws beyond the PTV). The only exception will be when observing the minimum field dimension of 3.5 cm when treating small lesions (see above). As such, prescription lines covering the PTV will typically be the 60-90% line (rather than 95-100%); however, higher isodoses (hotspots) must be manipulated to occur within the target and not in adjacent normal tissue. The isocenter in stereotactic coordinates will be determined from system fiducials (or directly from the tumor in the case of volumetric imaging) and translated to the treatment record. The treatment dose plan will be made up of multiple static beams or arcs as described above. The plan should be normalized to a defined point corresponding closely to the center of mass of the PTV (COMPTV). Typically, this point will be the isocenter of the beam rotation; however, it is not a protocol requirement for this point to be the isocenter. Regardless, the point identified as COMPTV must have defined stereotactic coordinates and receive 100% of the normalized dose. Because the beam apertures coincide nearly directly with the edge of the PTV (little or no added margin), the external border of the PTV will be covered by a lower isodose surface than usually used in conventional radiotherapy planning, typically around 80% but ranging from 60-90%. The prescription dose will be delivered to the margin of the PTV and fulfill the requirements below. As such, a "hotspot" will exist within the PTV centrally at the COMPTV with a magnitude of prescribed dose times the reciprocal of the chosen prescription isodose line (i.e., 60-90%).

### Intensity Modulated Radiation Therapy (IMRT)

IMRT is allowed in this study. The NCI Guidelines for the Use of IMRT can be found on the RTOG homepage, <http://www.rtog.org/>. The use of IMRT in this study is at the discretion of the treating radiation oncologist. IMRT should be considered only when target coverage, OAR dose limits, or dose spillage are not achievable with 3D conformal planning. In addition, IMRT plans should follow the same planning principles as discussed above for 3D conformal planning. The number of segments (control points) and the area of each segment should be optimized to ensure deliverability and avoid complex beam fluences. Ideally, the number of segments should be minimized (2-3 segments per beam should be adequate), and the

area of each segment should be maximized (the aperture of one segment from each beam should correspond to the projection of the PTV along a beam's eye view).

#### **6.4 Interruption and discontinuation**

Treatment delays are occasionally encountered during radiation therapy due to logistic problems (e.g. machine break downs, patient transportation issues) or public holidays. If this occurs radiation therapy shall be completed as soon as possible.

#### **6.5 Visit Schedule**

##### **6.5.1 Pre-Study Clinical Laboratory Tests and Procedures**

Prior to study treatment each patient will have the following assessments.

Within 4 weeks of starting study treatment:

- Radiologic studies for baseline tumor measurements with CT or MRI scanning (PET/CT is optional)
- History and physical exam
- CBC
- CMP
- Thyroid function and ACTH
- Urinalysis
- Serum pregnancy test
- Blood collection for correlative endpoints

##### **Within 3 days prior to first ipilimumab infusion**

- **Urine or Serum pregnancy test for WOCBP**

##### **6.5.2 On-Study Clinical Laboratory Tests and Procedures**

Before ipilimumab infusion:

- Evaluation for adverse events
- CBC and CMP
- Blood collection for correlative endpoints (before 2nd and 3rd ipilimumab infusion, before initiation of SABR)

##### **6.5.3 Follow-up Clinical Laboratory Tests and Procedures**

Thirty days after 4th ipilimumab infusion (+/- 20 days) with the goal of 30 days for the first visit

- History and physical examination
- Evaluation for adverse events
- CBC and CMP

- Blood collection for correlative endpoints: Week 12, 16, 20, 24, 35, and 50 (+/-20 days)

## **6.6 Study Procedures By Visit and Treatment Cycle**

Note that results of all safety laboratory tests (that is, all chemistry and all hematology results) must be obtained and reviewed before ipilimumab administration, as applicable. All laboratory results must be within the established range before ipilimumab is administered. All induction period laboratory samples must be collected within a window of up to 4 weeks before administration of ipilimumab. Laboratory evaluations using a local laboratory must be performed and the result examined by the investigator before administration of each dose of ipilimumab.

### **6.6.1 Study Completion or Early Discontinuation Visit**

At the time of study early withdrawal, the reason for early withdrawal and any new or continuing adverse events should be documented.

### **6.6.2 Study Drug Discontinuation**

If study drug administration is discontinued, the reason for discontinuation will be recorded.

## **6.7 Study Materials**

Bristol-Myers Squibb (BMS) will provide ipilimumab at no cost for this study.

## **6.8 Safety Assessments**

All patients who receive at least one dose of ipilimumab will be considered evaluable for safety parameters. Additionally, any occurrence of non-SAE or SAE from time of consent forward, up to and including follow-up visits, will be reported. See Section 8: Adverse Event Reporting.

Safety will be evaluated for all treated patients using the National Cancer Institute (NCI) Common Terminology Criteria for Adverse Events (CTCAE), Version 4.0 (<http://ctep.cancer.gov>). Safety assessments will be based on medical review of adverse event reports and the results of vital sign measurements, physical examinations, and clinical laboratory tests.

## **6.9 Adverse events**

The types of expected adverse events of SABR are directly related to the anatomical site being treated with SABR:

Lung SABR:

Expected acute toxicities- cough, dyspnea, fatigue

Possible sub-acute toxicities- radiation pneumonitis, rib fracture, chest wall pain

Liver SABR:

Expected acute toxicities- fatigue, diarrhea, increase in LFT's, nausea, vomiting

Possible sub-acute toxicities- chronic LFT elevation, gastric ulcer, duodenal ulcer, liver dysfunction

Spine SABR:

Expected acute toxicities- fatigue, nausea, vomiting, diarrhea

Possible sub-acute toxicities- radiation myelitis, vertebral fracture

Adrenal SABR:

Expected acute toxicities- fatigue, nausea, vomiting, diarrhea

Possible sub-acute toxicities- small bowel ulceration, small bowel obstruction

Nodal SABR:

Expected acute toxicities- fatigue, skin erythema, nausea, vomiting, diarrhea

Possible sub-acute toxicities- skin fibrosis, small bowel ulceration, small bowel obstruction

Brain stereotactic radiosurgery

Expected acute toxicities- headache, fatigue

Possible sub-acute toxicities- seizure, cerebral radionecrosis

Information about all adverse events, whether volunteered by the subject, discovered by investigator questioning, or detected through physical examination, laboratory test or other means, will be collected and recorded and followed as appropriate.

An adverse event is the appearance or worsening of any undesirable sign, symptom, or medical condition occurring after starting the study drug even if the event is not considered to be related to study drug. Medical conditions/diseases present before starting study drug are only considered adverse events if they worsen after starting study drug. Abnormal laboratory values or test results constitute adverse events only if they induce clinical signs or symptoms, are considered clinically significant, or require therapy.

The occurrence of adverse events should be sought by non-directive questioning of the patient at each visit during the study. Adverse events also may be detected when they

are volunteered by the patient during or between visits or through physical examination, laboratory test, or other assessments. As far as possible, each adverse event should be evaluated to determine:

1. the severity grade (mild, moderate, severe) or CTCAE v4.0 criteria (grade 1-4)
2. its relationship to the study drug(s) (suspected/not suspected)
3. its duration (start and end dates or if continuing at final exam)
4. action taken (no action taken; study drug dosage adjusted/temporarily interrupted; study drug permanently discontinued due to this adverse event; concomitant medication taken; non-drug therapy given; hospitalization/prolonged hospitalization)
5. whether it constitutes a serious adverse event (SAE)

All adverse events should be treated appropriately. Such treatment may include changes in study drug treatment including possible interruption or discontinuation, starting or stopping concomitant treatments, changes in the frequency or nature of assessments, hospitalization, or any other medically required intervention. Once an adverse event is detected, it should be followed until its resolution, and assessment should be made at each visit (or more frequently, if necessary) of any changes in severity, the suspected relationship to the study drug, the interventions required to treat it, and the outcome.

## **6.10 Definition of Efficacy Assessments**

- Rate of progression-free survival of ipilimumab and SABR in patients with oligometastatic melanoma as measured from the time of study enrollment until the first documented date of disease progression by both mWHO and irRC criteria.
- Frequency of grade 3 and grade 4 toxicities according to CTCAE (Common Toxicity Criteria for Adverse Events) version 4
- Frequency of objective response rate, defined as complete response + partial response, measured by mWHO criteria based on radiographic response rate will be determined based on re-staging CT of the chest, abdomen and pelvis
- Frequency of objective response rate, defined using the immune related response criteria (irRC) based on radiographic response rate will be determined based on re-staging CT of the chest, abdomen and pelvis
- Rate of local failure, as measured from the time of study enrollment until the first documented date of failure within the irradiated field
- Rate of overall survival, as measured from the time of study enrollment until the time of death

Biopsy, clinical evidence and radiographic evidence are all acceptable and will be used to document progression.

Overall survival: will be calculated as the time from entry on the study until the time of death.

Re-staging imaging with contrast-enhanced CT or MRI of the chest, abdomen, and pelvis will be performed before treatment, prior to 3rd ipilimumab infusion, 4 weeks after the final ipilimumab infusion (week 14 if there are no interruptions), and every 3 months for the first 2 years, then every 6 months during years 2-5.

The first re-staging scans after the week 14 imaging will be done at the 6 months from enrollment time point so that the endpoint of 6 month progression-free survival can be assessed.

All patients that have been treated on protocol with SABR and ipilimumab will have re-staging imaging even if they were taken off of protocol for adverse events after the SABR. Patients who do not have SABR due to adverse events from the first 2 infusions of ipilimumab are not required to complete re-staging imaging.

Patients who meet the criteria for Complete Response or Partial Response will have a re-imaging 4-weeks later to confirm the response.

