SABR will be delivered between the second and third doses of ipilimumab (usually week 5-6 if no delays for ipilimumab toxicity) using the following suggested schedules: 18 Gy x 3 to peripheral lung, 10 Gy x 5 to central lung, 10 Gy x 5 to liver, 6 Gy x 5 to nodal stations, 12 Gy x 3 to adrenal, 24 Gy x 1 brain < 2 cm, 18 Gy x 1 brain 2-3 cm, and 15 Gy x 1 brain > 3 cm, 16-18 Gy x 1 to vertebral sites.

Duration of therapy: Patients will receive at least 12 weeks of therapy and will be observed for toxicity for 90 days after the last ipilimumab infusion. Patients will remain on study until evidence of progression by both mWHO and irRC or death. Patients in whom new lesions develop or baseline lesions grow will receive additional ipilimumab treatments to complete induction therapy.

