### **3.2 Primary Study Endpoints**

- Rate of progression-free survival of ipilimumab and SABR in patients with oligometastatic melanoma as measured from the time of study enrollment until the first documented date of disease progression by mWHO criteria

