## **6.0 STUDY PROCEDURES**

### **6.1 Treatment overview**

We will evaluate the combination of ipilimumab and SABR in patients with oligometastatic melanoma in this phase II trial.

The study will consist of the following schedule: ipilimumab will be administered on week 1 at a dose of 3 mg/kg.

Subsequent cycles of ipilimumab will be given every three weeks (week 4, 7, & 10).

SABR will be delivered between the second and third doses of ipilimumab (week 5-6) using the following suggested schedules: 18 Gy x 3 to lung, 10 Gy x 5 to liver, 6 Gy x 6 to nodal stations, 12 Gy x 3 to adrenal, 18 Gy x 1 to bone, and 24 Gy x 1, 18 Gy x 1, 15 Gy x 1 to < 2.0 cm, 2.0-3.0 cm, and >3 cm brain metastases, respectively.

Duration of therapy: Patients will receive at least 12 weeks of therapy and will be observed for toxicity for 90 days after the last ipilimumab infusion. Patients will remain on study until evidence of progression or death. Patients who meet criteria for reinduction therapy remain on study and re-induction is recommended if the criteria in Section 3.1.3 are met.

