## 7.0 STATISTICAL PLAN

### 7.1 Sample Size Determination

Overall, this study will require 32 evaluable patients. We estimate that we will accrue 1-2 patients per month; therefore, thus, the minimum study duration will be 16 months (2 accruals per month) and the maximum is 32 months (1 accrual per month for 32 patients).

Current literature and experience with ipilimumab in metastatic melanoma in this patient population shows that we can expect ipilimumab + SABR will not be considered promising in this patient population if at most 15% of patients are progression-free and alive at 6 months, because that is the expected 6 month PFS for ipilimumab alone. For this agent to be considered promising in this patient population, we would expect an improvement in the 6-month PFS rate to at least 35% with this regimen in this patient population. Constraining the Type I and II error rates to 10% each, the study design will require 32 evaluable patients to test these hypotheses regarding the 6-month PFS rate with ipilimumab when given in combination with the stereotactic ablative radiation therapy in this patient population. If we see at least 8 patients who have are alive and progression-free at 6 months after initiation of treatment out of the 32 evaluable patients, we will consider this sufficient evidence that this regimen has promising activity in this patient population. Otherwise, if 7 or fewer patients have are alive and progression-free at 6 months, we will consider this regimen to not be sufficiently active in this population of oligometastatic melanoma patients.

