### 7.2 Statistical methods

All evaluable patients will be included in calculating the 6-month PFS rate for the study along with corresponding 95% binomial confidence intervals (assuming the number of patients who are progression-free and alive at 6 months is binomially distributed). The numerator will be the number of patients at 6-months from enrollment who have either a complete response, a partial response, or stable disease (i.e. have not progressed) on re-staging imaging and who are alive. The denominator will be the number of patients on trial who received ipilimumab and SABR.

In addition, several secondary endpoints will be evaluated in these subjects:

- **Toxicity and Tolerability.** Frequency and severity of adverse events and tolerability of the regimen in each of the patient groups will be collected and summarized by descriptive statistics. As per NCI CTCAE v4.0, the term toxicity is defined as adverse events that are classified as either possibly, probably, or definitely related to study treatment. The maximum grade for each type of toxicity will be recorded for each patient, and frequency tables will be reviewed to determine toxicity patterns. In addition, we will review all adverse event data that

is graded as 3, 4, or 5 and classified as either “unrelated” or “unlikely to be related” to study treatment in the event of an actual relationship developing. The incidence of severe (grade 3+) adverse events or toxicities will be described. We will also assess tolerability of the regimens through assessing the number of patients who required dose modifications and/or dose delays. In addition, we will also capture the proportion of patients who go off treatment due to adverse reactions or even those who refuse further treatment for lesser toxicities that inhibit their willingness to continue participation on the trial. These tolerability measures will be assessed within each of the treatment arms and we will explore differences in these measures between the arms. All patients who have received at least one dose of any of the therapeutic agents in a treatment arm will be evaluable for toxicity and tolerability.

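### Section 6.10 sets one PFS event by both mWHO and irRC, which conflicts with the mWHO-only primary endpoint, and Section 7.2 names no criterion to settle who counts as a success

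*Combined protocol and SAP*

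**What the plan says.** **Primary endpoint.** The Study Summary and Sections 1.1 and 2.1 give a primary objective of PFS by mWHO. Section 3.2 measures it from enrollment "until the first documented date of disease progression by mWHO criteria". Section 3.3 lists PFS by irRC as a secondary endpoint.

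**Efficacy definitions.** Section 6.10 has one PFS bullet, running "until the first documented date of disease progression by both mWHO and irRC criteria". The same list gives objective response two bullets, one per criterion.

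**Staying on study.** Section 3.1.2 states: "Patients will remain on study until evidence of progression by both mWHO and irRC or death". Section 6.1 states the same rule without a criterion: "Patients will remain on study until evidence of progression or death".

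**Primary analysis.** Section 7.2 says: "The numerator will be the number of patients at 6-months from enrollment who have either a complete response, a partial response, or stable disease". The patient must also be alive. No response criterion is named there, in the Section 7.1 decision rule, or in the Kaplan-Meier PFS definition.

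**Null rate.** Under Section 7.1 the regimen "will not be considered promising in this patient population if at most 15% of patients are progression-free and alive at 6 months", and the reason given is "because that is the expected 6 month PFS for ipilimumab alone". The criterion behind the 15% is not stated.

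**The concern.** The two criteria treat new lesions differently. Under mWHO (Section 6.10.2) any new lesion is progression. Under irRC (Section 6.10.3) a new lesion alone is not; it enters the total tumor burden, which must rise by at least 25%. Stable disease, one of the categories that makes a patient a success in Section 7.2, therefore covers different patients under each system.

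Patients enter with one to three sites that SABR can target, and SABR is directed at those sites, so new lesions are a plausible main route of progression. Such a patient is a failure under Section 3.2 and may be a success under Section 6.10 read as a joint requirement.

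The trial has one arm, is open label and has one cut-off: 8 successes is promising, 7 is not. Reclassifying a single patient can reverse the conclusion, so the criterion should be fixed before data are seen.

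**Working it through.** **Step 1. Reproduce the design.** Inputs from Section 7.1: N = 32, success if X ≥ 8, null rate 15%, target rate 35%, both error rates limited to 10%. The Study Summary calls the design two-stage but gives no first-stage rule, so the single-stage rule in Section 7.1 is used.

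P(X ≥ 8 | p) = 1 − Σ (x = 0 to 7) C(32, x) pˣ (1 − p)³²⁻ˣ

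- p = 0.15: 0.0958 (type I error)
- p = 0.35: 0.918 (power)

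Both limits are met, so the stated design reproduces.

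**Step 2. Direction of any effect.** If both criteria must be met, the event date is the later of the mWHO and irRC progression dates. It cannot precede the mWHO date. A patient free of mWHO progression at six months is also free of joint progression, while the converse can fail. The success count under the joint reading is therefore equal to or greater than the mWHO count.

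Section 5.4 and Appendix III also describe irRC progression as needing two observations at least 4 weeks apart, whereas Section 6.10.3 only recommends confirmation in difficult cases. Under the former, progression first seen on the six-month scan could not be confirmed by that date.

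**Step 3. Size, by assumption.** The documents give no rate of mWHO progression without irRC progression at six months. Assume that 15% is the mWHO rate under an ineffective regimen, and that the joint definition raises the observed rate to p. Expected successes are 32p; each 5-point rise adds 32 × 0.05 = 1.6.

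| Rate p under the joint definition | Expected successes | P(X ≥ 8) |
|---|---|---|
| 15% (no shift) | 4.8 | 0.096 |
| 17.5% | 5.6 | 0.185 |
| 20% | 6.4 | 0.302 |
| 25% | 8.0 | 0.568 |

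**Step 4. Cost of keeping a joint definition.** If the null had to be raised to match, holding type I error at or below 10% with 32 patients would need:

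- null 20%: at least 10 of 32 (alpha 0.090, power at 35% = 0.732)
- null 25%: at least 12 of 32 (alpha 0.080, power at 35% = 0.449)

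**Step 5. Death.** Sections 3.2, 3.3 and 6.10 do not mention death in the PFS definition. Sections 7.1 and 7.2 require a success to be alive, and the Kaplan-Meier PFS in Section 7.2 counts death as an event. A death before six months cannot enter the numerator under any reading.

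**The case against.** The strongest reply is that Section 6.10 merely condenses Sections 3.2 and 3.3. Its bullets follow the same order, and the main structural change is that two PFS bullets become one. On the joint reading it would define neither the primary nor the secondary PFS endpoint, but a third that no objective names. Section 7.2 also speaks of best response under both criteria, where it clearly means each in turn. The phrase in Section 3.1.2 governs how long patients stay on study, not an endpoint. Read this way, nothing is inflated.

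Much of this stands. The primary criterion is consistent wherever the endpoint is set, and reading Section 6.10 as two analyses is reasonable. But the same list keeps separate bullets for the two response rates, gives PFS a single date, and shares its phrase with a rule in Section 3.1.2 that is plainly joint. Section 7.2, which should decide, names no criterion. The ambiguity remains.

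Three stronger readings are tempting but unsupported:

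- *That leaving out death inflates the primary count.* Step 5 rules this out. Section 3.2 omits death too, so the omission is not even a contrast with Section 6.10.
- *That the 15% null is an mWHO rate.* Section 7.1 attributes it only to ipilimumab alone, with a citation. Step 3 assumes it.
- *That every known lesion is irradiated, so nearly all progression is by new lesions.* The documents set a limit of one to three targetable sites; they do not say this outright.

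**Conclusion.** Section 6.10 is wrong as written: its single PFS event conflicts with the mWHO-only primary endpoint and the separate irRC secondary endpoint, and nothing in Section 7 resolves the conflict. The direction is certain on the joint reading, since successes can only stay equal or rise. The size is unknown. The range in Step 3, from 0.096 up to 0.568, rests on assumed shifts and on 15% being the mWHO rate. On the separate-analyses reading the effect is zero.

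A reader might infer that the trial's type I error is inflated. The documents support only that it could be, if the analysis followed Section 6.10 literally over the stated objective and Section 3.2. The missing mention of death is a wording inconsistency with no effect on the primary count. This should be fixed, but it does not undermine the design.

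**What to change.** 1. Split the PFS bullet in Section 6.10 into two: primary, time from enrollment to first mWHO progression or death from any cause; secondary, the same with irRC progression. Add death to Sections 3.2 and 3.3 to match.
2. Name mWHO as the criterion in the Section 7.2 numerator.
3. Reconcile the on-study statements in Sections 3.1.2 and 6.1, and state that time on study does not move the primary event date.
4. State in Section 7.1 which criterion underlies the 15% null.

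The cost is protocol wording only. No new data, scans or patients are needed, and with mWHO used throughout the design stays at 8 or more of 32, with alpha 0.096 and power 0.918.
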